9.3. Treatment Compliance

The Investigator should monitor the subject's IP dosing compliance on an ongoing basis, as confirmed by IP accountability. If the Investigator has concerns about a subject's dosing compliance, s/he should discuss this with the subject and/or parent/guardian, assess the reasons and whether the subject is likely to remain non-compliant. The Medical Monitor should be notified of any potential dosing compliance issues.

Dose adjustments in this trial are discouraged. However, if there is evidence of intolerance at the current dose, and the subject is experiencing clinical benefit, a dose reduction and/or drug holiday followed by re-introduction of study drug at a reduced dose may be considered after consultation with the Medical Monitor (see Section 6.4).

Subjects will be instructed to retain all bottles of IP, even if empty, and to return the bottles with any unused capsules to the home health nurse at each visit noted in Table 3. The Investigator will perform IP accountability and will follow-up with subjects to retrieve any IP supplies that have not been returned. The subject and/or parent/guardian will be instructed to take note of any missed doses and, if possible, to document this information and to report it at the time of their next visit.

9.4. Randomization and Blinding

This is a randomized, double-blind, crossover trial. Therefore, every subject will receive NB-001 and placebo. However, the subject and parent/guardian, the Investigator, clinical trial site personnel, home health nurses, centralized rater(s), and the Sponsor will be blinded to treatment sequence assignment.

Subjects will be randomized at the conclusion of the Screening Visit, after confirmation of trial eligibility. Randomization will occur in a 1:1 ratio to one of two treatment sequences: NB-001 followed by placebo (treatment sequence A/P) or placebo followed by NB-001 (treatment sequence P/A). The randomization scheme will be generated using a computer program and verified for accuracy using strict quality control procedures. Each IP bottle will be labeled with a unique bottle number which will correspond to the randomization code and blinded treatment assignment.

In the event of a medical emergency in which it is important for the treating physician to know the treatment assignment, the blind may be broken by the Investigator. When possible (i.e., if time allows), the Investigator will contact the Medical Monitor, or designee, prior to accessing the treatment code for the subject. Instructions for emergency unblinding of treatment codes by the Investigator will be provided separately.

10. INVESTIGATIONAL PRODUCT MATERIALS AND MANAGEMENT

10.1. Investigational Product

NB-001 is (5R)-5-(pyridine-1-carbonyl)pyrrolidin-2-one monohydrate; also known as fasoracetam monohydrate. Each NB-001 capsule contains 100 mg of the active ingredient. The capsules are size 1 and white in color.

Placebo capsules contain excipients only and match the NB-001 capsules in appearance.

10.2. Investigational Product Packaging and Labeling

NB-001 and matching placebo will be supplied to the Investigator or designee in blinded plastic bottles, each containing 40 capsules. Each bottle will be labeled with the protocol number, storage conditions, dosing instructions, the federal cautionary statement, a unique bottle number and the Sponsor name and address. Prior to dispensing IP to the subject, the Investigator or designee will annotate the label to include the subject number, Visit/Assessment, and date dispensed. Two bottles will be dispensed at each clinic visit noted in Table 3.

10.3. Investigational Product Storage

Until dispensing to the subject, NB-001 and placebo bottles will be stored in a locked and limited access area at room temperature (15-25°C). The subject and parent/guardian will be informed of appropriate storage requirements.

10.4. Investigational Product Preparation

NB-001 and placebo capsules require no preparation prior to dosing.

10.5. Investigational Product Administration

NB-001 or placebo capsules will be administered orally to the subject. Subjects will take 2 capsules BID, 2 in the morning and 2 in the evening (i.e., 4 capsules daily). The subject should begin dosing for Treatment Period 1 on the morning of Day 1, after collection of pre-dose samples. If Day 0 and Day 1 are combined, the Investigator should schedule the combined Day 0/Day 1 visit early enough in the morning to ensure all Day 0 procedures are completed, pre-dose samples collected, and the total daily dose is taken (2 capsules, BID; 4 capsules total), in that order. Similarly, the subject should begin dosing for Treatment Period 2 on the morning of Day 50 after collection of pre-dose samples. If Day 49 and Day 50 are combined, the Investigator should ensure that the procedures required for Day 49 are completed at the end of the wash-out period and prior to pre-dose sample collection and dosing.

Capsules may be either swallowed whole or, if the subject is unable to swallow a capsule whole, it may be opened, and its contents sprinkled on applesauce. If the subject can swallow the capsules intact, sufficient liquids should be taken to swallow the capsule. If dosing is delayed, the subject should take the dose as soon as remembered with a minimum of 4 hours between doses. For example, if the subject forgets to take the morning dose and takes it upon

remembering in the afternoon, the subject should wait at least 4 hours before taking his/her evening dose. Missed doses should be reported to the Investigator.

Dosing will be paused from Days 43-49, during the wash-out period. No capsules will be taken during this time. The wash-out period may be extended beyond one week (and within reason) to accommodate the subject's schedule, after consultation with the Clinical Research Associate (CRA) or Medical Monitor.

10.6. Investigational Product Accountability

Both NB-001 and placebo will be provided in quantities sufficient for subject enrollment. Subjects and parents/guardians will be instructed to return all IP bottles, including empty bottles and bottles containing unused capsules, at each visit noted in Table 3, and the Investigator or designee will review the record of returned IP and assess compliance.

The Sponsor and Investigator will ensure that records of IP inventory and accountability are maintained throughout the trial. IP supplies and records must be readily available for inspection by the Sponsor or its representatives and regulatory authorities at any time.

10.7. Investigational Product Handling and Disposal

All unused IP will be recorded by the Investigator and reconciled by the Clinical Research Associate (CRA) on an ongoing basis throughout the trial. The Sponsor will provide instructions regarding IP disposal.

11. ASSESSMENTS OF EFFICACY

All symptom scales included in this section are either "clinician rated" or may be proctored by a local clinician, and will be administered centrally and, when possible (i.e., optional), locally, i.e., by the clinical trial Investigator or delegate, via telemedicine. The telemedicine sessions may be recorded, and the central and local assessments conducted concurrently or, for the local rater, asynchronously (after review of the audio recording). Assessment will be conducted by licensed clinicians, defined as a Doctor of Medicine, Doctor of Osteopathic Medicine, licensed psychologist with a PhD or PsyD, or highly trained BA or MA level raters under PhD/MD supervision as otherwise approved by the Sponsor. Scoring guidelines for the rating scales will be provided in a separate document. Whenever possible, the same central and, if applicable, local rater should administer all scales to a given subject and/or parent/guardian at each visit throughout the subject's participation in the trial. The parent/guardian and clinician should be available to answer any questions that the raters may have. Efforts should be made, when possible, to complete assessments in the same, consecutive order at each visit and as listed in Table 3.

In addition to the validated rating scales below, the subject and/or parent/guardian will be asked about the impact on the subject by the COVID-19 pandemic or other stressors and/or significant changes in the subject's life that may impact behavior, positively or negatively.

11.1. Clinical Global Impression Scales

The CGI scales will be performed by a central rater and, when possible, by a local rater and will be the last assessment performed at each visit. A rating of the CGI-S and/or CGI-I by the local rater is optional. In order to complete the CGI-S and/or CGI-I rating, the local rater must participate in the PARS interview or review the audio recording of the PARS interview. CGI-I assessments at Assessment Days 14, 28, 42 and 49 should use the Assessment Day 0 CGI-S baseline rating as reference for change. CGI-I assessments at Assessment Days 63, 77, 91 and 119 should use the Assessment Day 49 CGI-S baseline rating as reference for change. When possible, the same central and, if applicable, local raters will complete all CGI scales for a given subject throughout the subject's trial participation.

The CGI-S scale will be used to establish the degree of disease severity for each subject. The CGI-I scale will be used as an outcome measure for estimating level of functioning in response to treatment. The clinician's global assessments of the severity of the symptoms and changes in symptoms from baseline (Day 0 or Day 49, per above) will be based on reports from the subject and/or parent/guardian, and minimal direct observation (Guy 1976; Busner and Targum 2007).

The CGI-S scale will be administered at Screening and Day 0 prior to dosing, and at additional visits noted in Table 3, to rate the severity of the subject's condition on a 7-point scale ranging from 1 (Normal, not at all ill) to 7 (Among the most extremely ill subjects) (Appendix 1). At the visits noted in Table 3, the central and, if applicable, the local rater will assess the subject's improvement relative to his/her symptoms at baseline (Day 0 or Day 49, per above) using a CGI-I assessment, a 7-point scale ranging from 1 (very much improved) to 7 (very much worse) (Appendix 2).

Administration of the CGI scales is estimated to take 10 to 20 minutes.

11.2. Pediatric Anxiety Rating Scale

The PARS is a clinician-rated instrument for assessing, over time, the severity of anxiety symptoms that are associated with common DSM-5 (American Psychiatric Association 2013) anxiety disorders (GAD, separation anxiety disorder, and social phobia [SoP) in subjects aged 6 to 17 years. The clinician will interview both the subject and the parent/guardian to complete this assessment at the visits described in Table 3.

The PARS includes 2 sections. The first section is a 50-item symptom checklist, which the clinician rates as present or absent during the past week. The second section is comprised of 7 severity/impairment items that are rated on a 6-point Likert scale. The 7 severity/impairment items reflect the severity/impairment of all symptoms noted in Section 1 of the PARS (during the previous week) (Research Units on Pediatric Psychopharmacology Anxiety Study Group 2002). The PARS is provided in Appendix 3.

Administration of the PARS is expected to take 20 to 30 minutes and will be completed by the central rater and, when possible, by a local rater. A rating of the PARS by the local rater is optional. When possible local raters may participate in the PARS interview via telemedicine and/or asynchronously review the PARS interview audio recording to complete their PARS rating.

11.3. Attention Deficit Hyperactivity Disorder-Rating Scale-5

The ADHD-RS-5 will be administered at the visits noted in Table 3 to document the subject's ADHD symptoms over the previous week. The ADHD-RS-5 Home Version is a parent/guardianreported scale that was developed to measure the behaviors of children with ADHD, with separate forms for children (ages 5-10 years) and adolescents (11-17 years). The ADHD-RS-5 consists of 18 items designed to reflect the symptomatology of ADHD based on the DSM-5 criteria (American Psychiatric Association 2013). Each item will be scored on a scale ranging from 0 (reflecting no symptoms) to 3 (reflecting severe symptoms) with total scores ranging from 0 to 54.

The 18 items may be grouped into 2 subscales: inattention and hyperactivity/impulsivity. The Inattention subscale raw score is computed by summing the item scores for Items 1 through 9 and the Hyperactivity–Impulsivity subscale raw score is computed by summing the item scores for Items 10 through 18. Additionally, the ADHD-RS-5 incorporates 2 impairment scales keyed to the inattention and hyperactivity–impulsivity dimensions, which allow the clinician to assess the extent to which ADHD-related problems adversely affect the home and/or school functioning of children and adolescents (Appendix 4) (DuPaul et al. 2016).

Administration of the ADHD-RS-5 is expected to take 10 to 15 minutes and will be proctored by the local rater.

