7. SELECTION AND WITHDRAWAL OF SUBJECTS

7.1. Subject Inclusion Criteria

Subjects must meet all of the following subject inclusion criteria to be eligible to participate in the trial:

- 1. The subject has a genotype with a pathologic deletion in the 22q11 region confirmed by documentation (e.g., genetic test results) available at the clinical trial site.
- 2. The subject is aged 6 to 17 years old, inclusive.
- 3. The subject has a CGI-S scale score of ≥4 (i.e., moderately, markedly, severely, or among the most extremely ill patients) at Screening. Note that the Severity score of 4 could be from a composite of 2 or more sub-threshold scores.

And either:

- a. Psychiatric symptoms in the clinical range for **at least 1 of 3 disorders**, anxiety disorder, ADHD, or ASD, respectively, as demonstrated by score(s) at or above the following numbers *on at least 1 of 3 scales*:
 - PARS 5-Item Severity Score ≥ 12 (i.e., sum of items $2+3+5+6+7 \geq 12$)
 - ADHD-RS-5 Scores of 2 or 3 (i.e., "Often" or "Very Often") on at least 6 questions, with the majority of symptoms related to inattention (common in 22q11DS) rather than hyperactivity (less common in 22q11DS)
 SRSTM-2 >60

• SF

OR:

- b. Psychiatric symptoms in the **subclinical range for at least 2 of 3 disorders**, anxiety disorder, ADHD, and/or ASD, respectively, as demonstrated by scores at or above the following numbers *on at least 2 of 3 scales*:
 - PARS 5-Item Severity Score of 10 or 11 (i.e., sum of items 2+3+5+6+7=10 or 11)
 - ADHD-RS-5 Scores of 2 or 3 (i.e., "Often" or "Very Often") on 4 or 5 questions, with the majority of symptoms related to inattention (common in 22q11DS) rather than hyperactivity (less common in 22q11DS)
 - SRSTM-2 of 55-59
- 4. The subject has adequate renal and hepatic function indicated by:
 - Estimated glomerular filtration rate (eGFR) ≥60 mL/min/1.73 m² (per the revised Schwartz equation; Fadrowski and Furth 2011; Staples et al. 2010)
 - serum bilirubin ≤2.5 × upper limit of normal (ULN), unless documented Gilbert's Disease; aspartate aminotransferase and alanine aminotransferase ≤2.5 × ULN
- 5. If the subject is female and of reproductive potential, she has a negative serum pregnancy test at Screening and a negative urine pregnancy test on Day 0.
- 6. If the subject is of reproductive potential, s/he agrees to abstain from reproductive cell donation, per below, and, if ever heterosexually active, to use dual effective/highly

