11.4. Social Responsiveness Scale, Second Edition

The SRSTM-2 identifies the presence and severity of social impairment within the autism spectrum and differentiates it from that which occurs in other disorders. It is a 65-item, parent-

completed questionnaire which incorporates 5 content areas of social deficits: social awareness, social cognition, social communication, social motivation, and autistic mannerisms. The SRSTM-2 should be administered as described in Table 3, is estimated to take about 15-20 minutes to complete, and will be proctored by the local rater. (Appendix 5) (Constantino et al. 2003; Constantino and Gruber 2005).

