15.4. Efficacy Analyses

All statistical testing will be based on a 2-sided significance level of 0.05 and will be considered exploratory in nature. Efficacy results will be analyzed by treatment group. Data collected at

post-baseline evaluation time points will be combined across the 2 treatment periods depending on the treatment received, based on the following:

The baseline value will be the last measurement reported prior to the first dose of any IP at Day 1 during Treatment Period 1 or Day 50 during Treatment Period 2 and will be further defined in the SAP.

The treatment effect on the continuous efficacy endpoints, i.e., CGI-I and CGI-S and other efficacy endpoints, will be evaluated using mixed-effects models. A model will be defined for each endpoint to include treatment, visit, treatment-by-visit interaction, period and sequence as fixed effects, subject nested within sequence as a random effect, and the baseline value as a covariate. The within-subject errors will be modeled using an unstructured covariance matrix. The Kenward-Roger approximation will be used to estimate denominator degrees of freedom. If a model fails to converge, other covariance structures will be evaluated until model convergence is met.

Each efficacy endpoint will be first evaluated within the subset of subjects with the corresponding significant domain/symptom of greatest impairment, e.g., the treatment effect on the PARS will be assessed within the subset where the symptom of greatest impairment is anxiety. Additional analyses of the efficacy endpoints will be performed in the overall subject population.

A supportive analysis of the efficacy endpoints measured on an ordinal scale, including the CGI-I and CGI-S will be performed by comparing the treatment groups using a Wilcoxon signed-rank test at each post-baseline evaluation.

An overall treatment effect evaluation will be performed using the global test for multiple endpoints (O'Brien 1984; Dmitrienko and Tamhane 2009). This test relies on pooling the evidence of effectiveness across several endpoints and will be employed for assessing the evidence to support the global alternative hypothesis that NB-001 is uniformly better than placebo in the mean changes in the PARS, ADHD-RS-5, and SRSTM-2 scores (treated as 1 instrument).

Efficacy summaries will be based on observed data only and no explicit imputation to account for missing data will be performed.

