Appendix 5: Social Responsiveness Scale, Second Edition

| School-Age Form | Response Sheet | VVDS |
|-----------------|--------------------|---------------------|
| | SRS [®] 2 | unlocking potential |
| - | | |

Social Responsiveness Scale, Second Edition

[name]

Child and Rater Information

| Child s name | Gender | Date of rating | Assessment ID |
|------------------|----------------------|-------------------------|-------------------------|
| | Male Female | | 1 |
| School or clinic | | Child s age in years | Grade |
| Rater s name | Relationship to rate | ed Individual | |
| | D Mother DEathe | r Other custodial adult | Teacher Other specialis |

| nstructions: For each question, please circle the number that best describes this child s behavior over the past 6 months | Not True | Sometimes True | Often True | Almost Always True |
|---|-------------|-------------------|---------------|--------------------------|
| 1. Seems much more fidgety in social situations than when alone. | 1 | 2 | 3 | 4 |
| 2. Expressions on his or her face don t match what he or she is saying. | 1 | 2 | 3 | 4 |
| 3. Seems self-confident when interacting with others. | 1 | 2 | 3 | 4 |
| When under stress, he or she shows rigid or inflexible patterns of behavior that seem odd. | 1 | 2 | 3 | 4 |
| 5. Doesn t recognize when others are trying to take advantage of him or her. | 1 | 2 | з | 4 |
| 6. Would rather be alone than with others. | 1 | 2 | 3 | 4 |
| 7. Is aware of what others are thinking or feeling. | 1 | 2 | 3 | 4 |
| 8. Behaves in ways that seem strange or bizarre. | 1 | 2 | 3 | 4 |
| 9. Clings to adults, seems too dependent on them. | 1 | 2 | 3 | 4 |
| Takes things too literally and doesn t get the real meaning of a conversation. | 1 | 2 | 3 | 4 |
| 11. Has good self-confidence. | 1 | 2 | 3 | 4 |
| 12. Is able to communicate his or her feelings to others. | 1 | 2 | 3 | 4 |
| Is awkward in turn-taking interactions with peers (for example, doesn t seem to understand the give-and-take of conversations). | 1 | 2 | 3 | 4 |
| 14. Is not well coordinated. | 1 | 2 | 3 | 4 |
| Is able to understand the meaning of other people s tone of voice and facial expressions. | 1 | 2 | 3 | 4 |
| 16. Avoids eye contact or has unusual eye contact. | 1 | 2 | 3 | 4 |
| 17. Recognizes when something is unfair. | 1 | 2 | 3 | 4 |

ontinued on next page

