4.4.5 Secondary Endpoint Analysis Methods

The CGI-I per local rater, CGI-S per central rater, CGI-S per local rater, PARS Total Severity Score per central rater, PARS Total Severity Score per local rater, ADHS-RS-5 (Inattention and Hyperactivity Subscale Scores), and the SRSTM-2 Total Derived T-Score will be analyzed using the same statistical methodologies as applied to the primary efficacy endpoint, described in Section 4.4.4. For all endpoints where baseline is collected (i.e., excluding the improvement scales), the baseline value will be added as a covariate in the mixed-effects model.

The analyses for the CGI-I per central rater, CGI-S per central rater, PARS per central rater, ADHS-RS-5, and SRSTM-2 as described above will also be presented in separate summaries by treatment period. For these analyses, the mixed-effects model used to evaluate the treatment effect will include treatment, visit, and treatment-by-visit interaction as fixed effects and the baseline value as a covariate.

For all efficacy measures, mean scores over time will be plotted and presented by treatment group as well as by treatment sequence. Spaghetti plots will also be provided to show individual scores over time by treatment sequence.

For the CGI-I per central rater, scores collected during the washout and follow-up periods will be summarized by treatment sequence using descriptive statistics.

Confidential Page 20 of 28

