4.4.7.8 Examination of Subgroups

The efficacy analyses for PARS Total Severity Score per central rater, PARS Total Severity Score per local rater, ADHS-RS-5 (Inattention and Hyperactivity Subscale Scores), and SRSTM-2 Total Derived T-Score will be first evaluated within the subset of subjects with the corresponding significant domain/symptom of greatest impairment (e.g., the treatment effect on the PARS will be assessed within the subset where the symptom of greatest impairment is anxiety). The domain/symptom of greatest impairment will be determined at baseline using the psychiatric symptoms described below (inclusion criteria # 3 in Section 7.1 of the clinical study protocol):

- a) Psychiatric symptoms in the **clinical** range for at least one of three disorders (anxiety, attention/executive deficits, and social interaction/repetitive tendencies) as demonstrated by scores at or above the following numbers on at least 1 of 3 scales:
 - PARS 5-Item Severity Score ≥ 12
 - O ADHD-RS-5 Scores of 2 or 3 on at least 6 questions, with the majority of symptoms related to inattention rather than hyperactivity
 - SRSTM-2 Derived T-Score \geq 60; or
- b) Psychiatric symptoms in the **subclinical** range for at least two of three scales:
 - o PARS 5-Item Severity Score of 10 or 11
 - o ADHD-RS-5 Scores of 2 or 3 on 4 or 5 questions, with the majority of symptoms related to inattention rather than hyperactivity
 - SRSTM-2 Derived T-Score of 55-59.

Subjects may be counted in up to three subgroups, corresponding to any clinical or subclinical symptoms they report for the PARS, ADHD-RS-5, and SRSTM-2 scales. The six possible subgroups in which a subject may be counted are listed below:

Confidential Page 22 of 28

- Subjects with Anxiety Symptoms in the Clinical Range at Enrollment
- Subjects with Anxiety Symptoms in the Subclinical Range at Enrollment
- Subjects with ADHD Symptoms in the Clinical Range (Majority Related to Inattention) at Enrollment
- Subjects with ADHD Symptoms in the Subclinical Range (Majority Related to Inattention) at Enrollment
- Subjects with Autism Symptoms in the Clinical Range at Enrollment
- Subjects with Autism Symptoms in the Subclinical Range at Enrollment

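### ADHD-RS-5 recall is one week in the text but six months on the forms, and the SRS-2 has only its form's six months; followed literally, the forms dilute the crossover contrast toward no difference

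*Protocol*

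**What the plan says.** **ADHD-RS-5.** Protocol 11.3 says the scale is given at the Table 3 visits to document "ADHD symptoms over the previous week". SAP 3.4.1.2 says the same and sends the reader to Protocol Appendix 4 for further details. The child and adolescent forms printed there both ask the parent about the past six months.

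**SRS-2.** Protocol 11.4 says only that the scale "should be administered as described in Table 3, is estimated to take about 15-20 minutes to complete" and is proctored by the local rater. SAP 3.4.1.2 gives no recall window either. The only one is on the Appendix 5 form: "please circle the number that best describes this child s behavior over the past 6 months".

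**Schedule and use.** Table 3 lists both scales at Screening and at Days 0, 14, 28, 42, 49, 63, 77, 91 and 119. Both are secondary endpoints. The ADHD-RS-5 Inattention score and the SRS-2 T-score are two of the three components of the global test on mean change from baseline (SAP 4.4.7.5). Each period has its own baseline: "The baseline value will be the last measurement reported prior to the first dose of any IP at Day 1", or at Day 50 for Period 2 (Protocol 15.4). In the mixed model, "the baseline value will be added as a covariate in the mixed-effects model" (SAP 4.4.5).

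**Eligibility and subgroups.** Inclusion criterion 3 counts ADHD-RS-5 items scored 2 or 3 (clinical range: "on at least 6 questions, with the majority of symptoms related to inattention") and uses an SRS-2 cut-off. SAP 4.4.7.8 applies the same thresholds to subgroups: "The domain/symptom of greatest impairment will be determined at baseline using the psychiatric symptoms described below".

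**Guidance elsewhere.** Protocol 11 states: "Scoring guidelines for the rating scales will be provided in a separate document".

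**The concern.** For the ADHD-RS-5, the text and the forms give different windows, and neither document says which one governs. For the SRS-2 there is nothing to set against the form. Parents complete both scales, so the printed instruction is what the respondent reads.

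A crossover contrast needs each rating to describe the period in which it is made. A six-month question does not do that here. Ratings in Period 1 would be mixed with pre-trial time. In sequence A/P (NB-001 first), the Day 49 baseline and the Period 2 placebo ratings would still contain the 42 NB-001 days. At stake are two secondary endpoints and two thirds of the global test. The window used at Screening also matters, because the scores decide eligibility and subgroup membership.

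**Working it through.** **Inputs from the documents**

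- Participation (Protocol synopsis): 4 + 6 + 1 + 6 + 4 = 21 weeks, which reproduces the stated figure. Six months is 365.25 / 2 / 7 = 26.1 weeks, longer than the whole trial.
- NB-001 days: 1–42 in sequence A/P and 50–91 in P/A, with no dosing on Days 43–49. Six months is taken as 182 days: 182 / 42 = 4.3 treatment periods, and 182 / 91 = 2 double-blind phases.
- The documents give no figure for the effect of recall on these scales. The power statement is for CGI-I and does not bear on this point.

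**What a 182-day window contains**

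| Rating day | Pre-trial | Period 1 | Wash-out | Period 2 |
|---|---|---|---|---|
| 42 | 140 | 42 | 0 | 0 |
| 49 | 133 | 42 | 7 | 0 |
| 91 | 91 | 42 | 7 | 42 |

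**Model (assumed).** The drug effect is 1 on NB-001 days and 0 on all others, and a rating averages the days in its window evenly. Let s(sequence, day) be the share of the window spent on NB-001. Day 0 is 0 in both sequences.

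- Raw = ½{[s(A/P,42) − s(P/A,42)] + [s(P/A,91) − s(A/P,91)]}
- Change from baseline = Raw + ½[s(A/P,49) − s(P/A,49)]
- Baseline as a covariate with slope b: Raw + b × ½[s(A/P,49) − s(P/A,49)]. For b between 0 and 1 this lies between the first two.

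**182 days.** A/P at Days 42, 49 and 91: 42/182 = 0.231 each. P/A at Days 42 and 49: 0; at Day 91: 0.231.

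- Period 1: 0.231 − 0 = 0.231
- Period 2, raw: 0.231 − 0.231 = 0
- Raw crossover: (0.231 + 0)/2 = 0.115
- Change from baseline: 0.115 + 0.231/2 = 0.231
- Covariate model: 0.115 × (1 + b)

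**14 days.** Raw is 1.00. A/P at Day 49 covers Days 36–49, so s = 7/14 = 0.5, and change = 1.00 + 0.25 = 1.25.

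**Range of windows** (share of the true effect recovered, true = 1.00)

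| Recall, evenly averaged | Raw | Change from baseline | Period 1 only |
|---|---|---|---|
| 7 days | 1.00 | 1.00 | 1.00 |
| 14 days | 1.00 | 1.25 | 1.00 |
| 42 days | 1.00 | 1.42 | 1.00 |
| 56 days | 0.69 | 1.06 | 0.75 |
| 91 days | 0.23 | 0.46 | 0.46 |
| 182 days | 0.115 | 0.231 | 0.231 |

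The change contrast passes 1 between 58 days (1.009) and 59 days (0.983). If a 182-day recall is instead weighted toward recent days, raw / change is 0.84 / 1.15 for a half-life of 14 days, 0.53 / 0.80 for 30 days and 0.31 / 0.52 for 60 days.

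Every entry is a multiple of the true effect, so a true effect of zero gives zero in every row. No loss of power is quoted for the global test, because the SDs and correlations under long recall are not in the documents.

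**The case against.** The strongest defence is that Appendices 4 and 5 reproduce publishers' stock forms, that Protocol 11.3 and the SAP state the intended ADHD-RS-5 window, and that separate guidelines and a proctoring local rater may already tell parents to think of the past week. It stands this far: the documents cannot show that six months was ever the operative window. It does not remove the point. The guidelines are described as covering scoring, no text tells anyone to override the printed wording, and for the SRS-2 no other window is stated.

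Three stronger readings are tempting, and the documents do not support them.

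- *The direction of bias is unknown if the forms are followed.* At 182 days both the raw and the change contrasts shrink. Overstatement needs an effective recall of more than one week and less than about 58 days, which neither text nor form specifies, together with baseline adjustment. No raw contrast in the table exceeds 1. It remains possible in practice, because parents who rate repeatedly may dwell on recent weeks.
- *A positive result could not be trusted.* Under this model, zero true effect gives zero contrast. The size of an effect and the meaning of a null result become hard to read; a benefit is not manufactured.
- *Every rating mixes the two treatments.* Ratings at Days 14, 28 and 42 contain only pre-trial time and Period 1. SAP 4.4.5 already plans by-period analyses of both scales. The Period 1 comparison is randomised, has an untreated Day 0 baseline, and is diluted but still attributable to Period 1 treatment.

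**Conclusion.** The ADHD-RS-5 contradiction and the missing SRS-2 window are real and should be corrected. If the forms are followed literally, the end-of-period crossover contrast retains about 0.12 (raw) to 0.23 (change from baseline) of its true size, a loss of roughly 77% to 88% toward no difference. The Period 1 comparison alone retains 0.23. If effective recall is about 2 to 8 weeks, the change-from-baseline contrast could be moderately overstated through the A/P Day 49 baseline (1.06 to 1.42 at the windows tabulated).

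These figures rest on a constant effect that switches on and off with dosing, and on the assumed recall weighting. True recall is not observed.

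The weight is moderate. Both scales are secondary, efficacy testing is declared exploratory, and the primary objective is safety. The six-month wording does not reach CGI-I, which is anchored to the Day 0 or Day 49 CGI-S, or PARS, which asks about the past week.

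**What to change.** 1. **ADHD-RS-5.** Make the instruction used from Day 0 onward the past week, as Protocol 11.3 and the SAP already state. Change the wording of both forms if the licence allows; Appendix 4 carries a copyright notice, so this must be checked. Otherwise give a written instruction to the local rater who proctors the scale. State which window applies at Screening, where the score decides eligibility and subgroup. The cost is small: two form instructions or one rater instruction, plus one sentence in the protocol.

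2. **SRS-2.** State the recall window in Protocol 11.4 and SAP 3.4.1.2. If it stays at six months, add to the SAP that the crossover SRS-2 and global-test results are diluted toward no difference, that a null result is not evidence of no effect, and that the Period 1 by-period analysis in SAP 4.4.5 is the cleaner SRS-2 comparison. This costs a few sentences and no new data or analysis. Rewording the SRS-2 form is not requested: Appendix 5 requires the publisher's written permission for any adaptation, and a different recall window would depart from the basis of the T-score.

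If the separate scoring guidelines already set a past-week window, citing them in Protocol 11.3 and 11.4 and in the SAP would settle the window for the visits they cover.
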